6.4. Reference Start Date and Study Day

Study Day will be calculated from the reference start date, and will be used to show start/stop day of assessments and events.

Reference start date is defined as the day of the first dose of study medication, (Day 1 is the day of the first dose of study medication), and will appear in every listing where an assessment date or event date appears.

• If the date of the event is on or after the reference date then: Study Day = (date of event – reference date) + 1.

Document: CALIBR_CBR-KA34-3001_SAP_Final 1.0
Author: PPD Version Number: Final 1.0
Version Date: 15MAY2020

Template No: CE Reference: CE

Copyright © 2017 IQVIA. All Rights Reserved.

• If the date of the event is prior to the reference date then: Study Day = (date of event – reference date).

In the situation where the event date is partial or missing, Study Day, and any corresponding durations will appear partial or missing in the listings.

6.5. BASELINE

Baseline, is defined as the last scheduled non-missing measurement taken prior to the first dose.

6.6. RETESTS, UNSCHEDULED VISITS AND EARLY TERMINATION DATA

Unscheduled measurements will not be included in summary statistics, but will contribute to the assessment of clinical outliers. Early termination results will be recorded as such, and included with the end-of-study summaries.

In the case of a retest of a scheduled assessment, the earliest available measurement for that scheduled time (i.e. the original assessment) will be used for summaries unless flagged as invalid.

Listings will include all scheduled, unscheduled, retest and early discontinuation data.

6.7. COMMON CALCULATIONS

For quantitative measurements, change and percent change (as appropriate) from baseline will be calculated as:

- Change from baseline = Post baseline Value baseline Value, if baseline is not missing.
- Percent change from baseline = 100*[(Post baseline Value baseline Value)/baseline Value], if baseline if not missing.

6.8. SOFTWARE VERSIONS

All derivations, statistical analyses, summaries and listings will be generated using SAS Version 9.4 or higher (SAS Institute, Inc., Cary, North Carolina). Pharmacokinetic parameters will be derived using noncompartmental methods with the validated computer program Phoenix WinNonlin 8.0 or higher (Certara, L.P., Princeton, New Jersey, USA). Graphics will be prepared using the same versions of SAS.

Document: CALIBR_CBR-KA34-3001_SAP_Final 1.0

Author: PPD Version Number: Final 1.0

Version Date: 15MAY2020

Template No: CI Reference: CI Effective Date: 01Apr2016

Copyright © 2017 IQVIA. All Rights Reserved.

7. STATISTICAL CONSIDERATIONS

7.1. MISSING DATA

Missing safety data will not be imputed.

Missing PK concentrations will be handled as described in Section 15.

8. OUTPUT PRESENTATIONS

APPENDIX 1 shows conventions for presentation of data in outputs.

The table, listing, and figure shells provided with this SAP describe the presentations for this study and therefore the format and content of the summary tables, figures and listings to be provided by IQVIA Biostatistics and Pharmacokinetics/Pharmacodynamics Early Clinical Development.

9. DISPOSITION AND WITHDRAWALS

All subjects who provide informed consent will be accounted for in this study. For the SAD and MAD part, subject disposition will be tabulated for each dose levels and for all subjects overall with the number (%) of subjects who are randomly assigned to treatment, complete the study, prematurely discontinue, and the reason for early discontinuation. This summary will be provided for All Subjects Randomized Set. A listing will present dates of completion or early withdrawal and the reason for early discontinuation, if applicable, for each subject.

[figure not shown]
Listings of inclusion/exclusion criteria responses, study eligibility, treatment randomization, and study treatment administration will be provided for the SAD and MAD part.

10. Demographic and other Baseline Characteristics

Individual subject demographics, contraception review, urine drug screen data, Visual Analogue Scale (VAS) scores, Tibial-femoral radiographs status, magnetic resonance imaging (MRI), follicle-stimulating hormone [FSH] data and banked biospecimen collection details will be presented in listings for the SAD and MAD study part.

Demographic characteristics such as age, sex, race, ethnicity, height, weight, body mass index (BMI), affected knee location and grade of osteoarthritis will be summarized for the SAD and MAD part and tabulated by dose levels and for all subjects overall using the safety analysis set.

Descriptive statistics will be presented for age, height, weight, and BMI. Frequency counts and

Copyright © 2017 IQVIA. All Rights Reserved.

percentages will be presented for sex, race, ethnicity affected knee location and grade of osteoarthritis. No statistical testing will be carried out for demographic or other baseline characteristics.

10.1. DERIVATIONS

- BMI (kg/m²) = weight (kg)/ height (m)²
- Age (years) = Integer value of [(Date of informed consent date of birth + 1)/365.25]

11. PROTOCOL DEVIATIONS

11.1. DEVIATIONS RELATED TO STUDY CONDUCT

A protocol deviation is any noncompliance with the clinical trial protocol, Good Clinical Practice (GCP), or Manual of Procedure requirements. The noncompliance may be either on the part of the subject, the site Principal Investigator (PI), or the study site staff. Any subject enrolled who does not meet eligibility criteria will be considered an enrollment deviation. Protocol deviations will be listed including a classification of minor or major, as determined by clinical staff.

11.2. DEVIATIONS RELATED TO PHARMACOKINETIC AND PHARMACODYNAMIC ANALYSES

Changes to the procedures or events, which may impact the quality of the PK or PD data, will be considered significant protocol deviations and will be described within the clinical study report body text. These changes or events will include any circumstances that will alter the evaluation of the PK or PD variables. Examples include, but may not be limited to, incomplete dose delivered, sample processing errors that lead to inaccurate bioanalytical results, and/or inaccurate dosing on the day of PK or PD sampling. In the case of a significant protocol deviation or event, PK or PD data collected during the affected treatment period will be excluded from the study results. Other changes to the procedures or events which do not impact the quality of the PK data will not be considered significant protocol deviations. A common example of a non-significant protocol deviation is a missed blood sample or deviations from blood collection times.

Document: CALIBR_CBR-KA34-3001_SAP_Final 1.0
Author: PPD Version Number: Final 1.0
Version Date: 15MAY2020

Template No: C Reference: C

Effective Date: 01Apr2016

12. MEDICAL HISTORY

Medical History is collected and coded using Medical Dictionary for Regulatory Activities (MedDRA) Version 21.0 and will be presented for the safety analysis set.

Medical history will be listed and summarized by system organ class (SOC) and preferred term (PT) for each dose level and all subjects overall for the SAD and MAD study part.

13. MEDICATIONS

Medication usage is collected and coded using the World Health Organization (WHO) Drug Dictionary Version 01Mar2018 and will be presented for the safety analysis set.

- 'Prior' medications are medications which started and stopped prior to the first dose of study medication.
- 'Concomitant' medications are medications which were taken during the treatment period, or specifically:
- o Started after the first dose of study medication or
- o Started prior to the first dose of study medication and were continued after the first dose of study medication.

See APPENDIX 2 for handling of partial dates for medications, in the case where it is not possible to define a medication as prior or concomitant, the medication will be classified by the worst case; i.e. concomitant.

A subject listing of all prior and concomitant medications will be presented.

Concomitant medications will be summarized by preferred term for the SAD and MAD part by dose levels and all subjects overall.

14. STUDY MEDICATION EXPOSURE

Study medication administration data will be listed for the SAD and MAD part.

15. PHARMACOKINETIC ANALYSIS

For SAD and MAD parts, PK data will be listed for each dose levels with placebo subjects from all dose levels combined into a single, overall placebo group (presented as Placebo). Summaries will be

Document: CALIBR_CBR-KA34-3001_SAP_Final 1.0
Author: PPD Version Number: Final 1.0
Version Date: 15MAY2020

Template No: CE Reference: CE

Copyright © 2017 IQVIA. All Rights Reserved.

presented by Part (SAD or MAD) and by dose (SAD and MAD combined) for PK evaluations.

15.1. PLASMA CONCENTRATION DATA

Subjects with partial data will be evaluated on a case-by-case basis to determine if sufficient data are available for reliable estimation of PK parameters.

A listing of PK blood sample collection times as well as derived sampling time deviations will be provided for both single ascending and multiple ascending doses.

Pre-dose samples that occur before the first drug administration will be assigned a time of 0 hours, as if the sample had been taken simultaneously with the study drug administration.

Pharmacokinetic concentrations which are erroneous due to a protocol deviation (Section 11.2 and as defined in the study protocol), documented handling error or analytical error (as documented in the bioanalytical report) may be excluded from the PK analysis if agreed upon prior to performing a statistical analysis. In this case, the rationale for exclusion must be provided in the Clinical Study Report (CSR). Any other PK concentrations that appear implausible to the Pharmacokineticist/PKPD Data Analyst must not be excluded from the analysis. Any implausible data will be documented in the CSR.

Plasma concentrations will be summarized using descriptive statistics for each active treatment by dose. Concentrations that are below the limit of quantitation (BLQ) will be treated as zero for the computation of descriptive statistics. Lower limit of quantitation for KA34 will be identified in the bioanalytical data of plasma concentrations. Missing concentrations (e.g., no sample, insufficient sample volume for analysis, no result, or result not valid) will be reported and displayed generally as "N.R.". Samples that are collected outside the specified time windows will be included in the PK analysis (actual collection time is used in the parameter analysis) but excluded from the concentration summaries. The PK sampling collection schedule is presented in the Table below.

For the MAD part of the protocol, trough samples will be listed and summarized by dose. Steady-state assessment will be assessed by visual inspection of the mean trough concentration vs time plots (linear scale if concentrations are present). It is expected that the parent drug will not be present in plasma in a quantifiable concentration after 4 hours postdose.

A subject listing of all concentration-time data for each dose levels will be presented. Figures of arithmetic mean concentration-time data (±SD, as appropriate) will be presented by dose levels on linear and semi-logarithmic scales. Individual subject concentration-time data will be graphically presented on linear and semi-logarithmic scales.

SAD: Day 1 PK Sampling Schedule

COLLECTION TIME ALLOWABLE WINDOW

Pre-Dose Within 2 hours prior to IP administration

Document: CALIBR CBR-KA34-3001 SAP Final 1.0 Author: Version Number: Final 1.0 PPD Version Date: 15MAY2020

Template No: CC Effective Date: 01Apr2016 Reference: CC

Copyright © 2017 IQVIA. All Rights Reserved.

15 Minutes Post-Dose	+/- 2 Minutes
30 Minutes Post-Dose	+/- 3 Minutes
60 Minutes Post-Dose	+/- 5 Minutes
90 Minutes Post-Dose	+/- 5 Minutes
2 hours Post-Dose	+/- 5 Minutes
4 hours Post-Dose	+/- 5 Minutes

MAD: PK Sampling Schedule

Day	COLLECTION TIME	ALLOWABLE WINDOW
1	Pre-Dose	Within 2 hours prior to IP administration
	15 Minutes Post-Dose	+/- 2 Minutes
	30 Minutes Post-Dose	+/- 3 Minutes
	60 Minutes Post-Dose	+/- 5 Minutes
	90 Minutes Post-Dose	+/- 5 Minutes
	2 hours Post-Dose	+/- 5 Minutes
	4 hours Post-Dose	+/- 5 Minutes
8-29	Pre-Dose	+/- 1 Day

15.2. PHARMACOKINETIC PARAMETERS

For PK parameter calculations, both single ascending and multiple ascending dose groups will be summarized by dose as all PK parameters are on Day 1. Predose samples that are BLQ or missing will be assigned a numerical value of zero. Any anomalous concentration values observed at predose will be identified in the study report and used for the computation of PK parameters.

Any other BLQ concentrations will be assigned a value of zero if they precede quantifiable samples in the initial portion of the profile. A BLQ value that occurs between quantifiable data points, especially prior to C_{max}, will be evaluated to determine if an assigned concentration of zero makes sense, or if exclusion of the data is warranted. Following C_{max}, BLQ values embedded between 2 quantifiable data points will be treated as missing when calculating PK parameters. If a BLQ value occurs at the end of the

CALIBR CBR-KA34-3001 SAP Final 1.0 Document: Author: Version Number: Final 1.0 PPD 15MAY2020 Version Date: Template No: CC Reference: CC Effective Date: 01Apr2016

collection interval (after the last quantifiable concentration), it will be set to zero. If consecutive BLQ concentrations are followed by quantifiable concentrations in the terminal portion of the concentration curve, these quantified values will be excluded from the PK analysis by setting them to missing, unless otherwise warranted by the concentration-time profile.

The following PK parameters will be estimated for KA34 in plasma by non-compartmental methods using actual elapsed time from dosing. Day 1 PK parameters will be derived for both SAD and MAD doses. A minimum of 3 quantifiable concentration-time data points will be required for calculation of PK parameters:

 C_{max} Maximum concentration in the sampled matrix (ng/mL), obtained directly

from the observed concentration versus time data.

C_{max}/dose Dose adjusted C_{max} (ng/mL/ug)

 T_{max} Time of maximum concentration (h), obtained directly from the observed

concentration versus time data.

AUC_{0-t} Area under the concentration-time curve in the sampled matrix from zero

(predose) to time of last quantifiable concentration (ng·h/mL), calculated

by linear up/log down trapezoidal summation.

AUC_{0-t}/dose Dose adjusted AUC_{0-t}

AUC_{0-inf} Area under the concentration-time curve in the sampled matrix from zero

> (predose) extrapolated to infinite time (ng·h/mL), calculated by linear up/log down trapezoidal summation and extrapolated to infinity by addition of the last quantifiable concentration divided by the elimination

rate constant: $AUC_{0-t} + C_{last}/\lambda_z$.

AUC_{0-inf}/dose Dose adjusted AUC_{0-inf} (ng·h/mL/ug)

 λ_{z} Apparent terminal rate constant (1/h), determined by linear regression of

the terminal points of the log-linear concentration-time curve. Visual assessment will be used to identify the terminal linear phase of the concentration-time profile. A minimum of 3 data points will be used for

determination.

Apparent terminal half-life (h), determined as $ln2/\lambda_z$. $t_{1/2}$

CL/F Apparent systemic clearance after extravascular dosing (L/h), calculated as

dose divided by AUC_{0-inf}.

Vz/F Apparent volume of distribution following extravascular dosing (L),

calculated as dose divided by $[\lambda_z \cdot AUC_{0-inf}]$

Document: CALIBR CBR-KA34-3001 SAP Final 1.0

Author: Version Number: Final 1.0 PPD 15MAY2020 Version Date:

Template No: CCI Effective Date: 01Apr2016

The following PK parameters will be calculated for diagnostic purposes and listed but will not be summarized.

 $t_{1/2}$, Interval The time interval (h) of the log-linear regression to determine λ_z .

 $t_{1/2}$, N Number of data points included in the log-linear regression analysis to

determine λ_z . A minimum of 3 data points will be used for determination.

Rsq Goodness of fit statistic for calculation of λ_z (Regression coefficient).

%AUC_{ex} Percentage of AUC_{0-inf} obtained by extrapolation, calculated as

[(C_{last}/λ_z)/AUC_{0-inf}×100]. If the %AUC_{ex} is greater than 20.0% of AUC_{0-inf}, then AUC_{0-inf} will be listed but not included in summary and inferential

statistics.

Pharmacokinetic parameters will be summarized by dose levels using descriptive statistics. Geometric mean will not be calculated for T_{max} ; n, minimum, median and maximum will be presented. A subject listing of individual PK parameters for each dose levels will be provided.

A data listing identifying subjects with the following criteria will also be provided to identify subjects with $\text{%AUC}_{ex} > 20.0\%$, and Rsq <0.800.

Vertical point plots of individual and geometric mean for primary dose normalized PK parameters ($C_{max}/dose$, $AUC_{0-t}/dose$, and $AUC_{0-inf}/dose$) versus dose will be presented. Additional, graphical presentations of PK data may be added at the discretion of the PK scientist, if further illustration of the PK results is deemed appropriate.

Primary PK variables include AUC_{0-t}, AUC_{0-inf}, and C_{max}. All other parameters are secondary variables.

The dose proportionality of the primary PK parameters AUC_{0-t}, AUC_{0-inf}, and C_{max} summarized by dose delivered, will be assessed statistically using the following power model;

log(parameter) = a + b * log(dose)

where 'a' is the intercept and 'b' is the slope.

The Day 1 data from both SAD and MAD part may be combined as appropriate for the power model analysis. The intercept 'a' and the slope 'b' together with 90% confidence intervals will be estimated and presented for each PK parameter. A minimum of 3 values per dose must be available for a given parameter to estimate dose proportionality with the power model. Dose proportionality analysis will not be performed for the secondary PK parameters.

Document: CALIBR CBR-KA34-3001 SAP Final 1.0

Author: PPD

Version Number: Version Date:

Final 1.0 15MAY2020

Template No: CC

Effective Date: 01Apr2016

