3. STUDY DESIGN

3.1. **GENERAL DESCRIPTION**

This is a randomized, double-blind, placebo-controlled study to assess the safety, tolerability, pharmacokinetics, and pharmacodynamics of KA34 when administered via intra-articular injection to

CALIBR CBR-KA34-3001 SAP Final 1.0 Document: Author: Version Number: Final 1.0 PPD Version Date: 15MAY2020 Template No: CC

Effective Date: 01Apr2016

subjects with osteoarthritis of the knee. All subjects will receive a 5 mL injection of KA34 or placebo in the affected knee.

The study will consist of approximately 7 cohorts of subjects who will be randomized to receive KA34 or placebo. KA34 will be provided as a solution with a concentration of 200 µg per mL.

KA34 will be administered as a single dose to the following cohorts:

COHORT	DOSE	N PER COHORT
1	50 μg per knee	4 (3 – Active & 1 Placebo)
2	100 μg per knee	4 (3 – Active & 1 Placebo)
3	200 μg per knee	8 (6 – Active & 2 Placebo)
4	400 μg per knee	8 (6 – Active & 2 Placebo)

The decision to escalate to the next dose cohort will be made by the sponsor, based on the recommendation of the Data Safety Monitoring Board (DSMB), following a (blinded) review of all available safety information from Day 8 post-dose of the preceding dose cohort.

Once the safety and tolerability of single doses of KA34 have been assessed, multiple-dose administration of KA34 will be evaluated. The multiple-dose portion of the study will be initiated after a thorough review of the Day 29 safety data from the single-dose cohorts. During the multiple dose portion of the study, KA34 will be administered as 4 weekly doses to the following cohorts:

COHORT	DOSE	N PER COHORT
5	100 μg per knee per injection	12 (9 – Active & 3 Placebo)
6	200 μg per knee per injection	12 (9 – Active & 3 Placebo)
7	400 μg per knee per injection	12 (9 – Active & 3 Placebo)

The doses administered to subsequent cohorts in either the single or multiple dose portions of the study may be lowered if any safety or tolerability issues are identified which suggest that the planned doses may pose a risk to study participants. Additional dose groups may be added to the study depending on the observed safety and tolerability profile of KA34 or if the pharmacokinetic data permit a higher than anticipated dose while remaining within a safe exposure limit based on the toxicokinetics and safety profile from the nonclinical toxicology studies.

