5.3. PHARMACOKINETIC ANALYSIS SET

The pharmacokinetic analysis set will consist of all subjects who receive KA34 and have at least 1 measured concentration at a scheduled PK time point after start of dosing without protocol violations or events with potential to affect the pharmacokinetic concentrations. Subjects in this population will be used for all PK parameter analyses.

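### SAP 15.2: as worded, the three-sample minimum also withholds Cmax, Cmax/dose and Tmax, which need only one quantifiable sample (minor)

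*SAP*

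**What the plan says.** - SAP 15.2: "A minimum of 3 quantifiable concentration-time data points will be required for calculation of PK parameters". The sentence ends in a colon and leads into the parameter list. Cmax, Cmax/dose and Tmax come first, with no exception. The same list describes Cmax and Tmax as taken directly from the observed data.
- SAP 15.2, on λz: "A minimum of 3 data points will be used for determination".
- SAP 5.3 admits to the PK set subjects who received KA34 and "have at least 1 measured concentration at a scheduled PK time point after start of dosing", and uses that set for every PK parameter analysis.
- SAP 15.1: "Subjects with partial data will be evaluated on a case-by-case basis", to judge whether the data are sufficient. No parameter is named and no exception is given.
- SAP 15.1: "It is expected that the parent drug will not be present in plasma in a quantifiable concentration after 4 hours postdose".
- SAP 15.2, on dose proportionality: "A minimum of 3 values per dose must be available for a given parameter to estimate dose proportionality with the power model". Cmax is one of three primary PK variables. The section does not say whether a dose below that number is left out or the model is not fitted.
- SAP 6.1: a group with fewer than 2 values is shown as N/A.
- SAP 3.1: the 50 µg cohort has 3 active subjects, and no multiple-dose cohort receives 50 µg.
- Protocol 9.3 lists the PK parameters with no minimum number of samples.

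**The concern.** A three-point minimum is sensible for a fitted terminal slope or an area. It has no estimation purpose for a maximum that is simply observed. Applied to Cmax, it discards values that were measured, and not at random: the subjects with only one or two quantifiable samples are those with the lowest exposure, mostly at the lowest dose. Their Cmax leaves the geometric mean and the power model while higher values stay.

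What is at stake is a secondary analysis. The 50 µg Cmax summary could be too high or not shown. The 50 µg dose could leave the dose-proportionality model. The estimated Cmax slope could be too low. Protocol 1.2.1 reports low plasma levels and rapid clearance after intra-articular dosing in animals, which makes sparse profiles at 50 µg plausible but does not establish them.

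**Working it through.** The minimum is a convention, so there is no derived figure to reproduce. The cohort table does add up: 4+4+8+8+12+12+12 = 60.

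**1. What the general rule adds.**

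| Parameters | Quantifiable samples needed | Own minimum in SAP 15.2 | Added by the general rule |
|---|---|---|---|
| Cmax, Cmax/dose, Tmax | 1 | none | withheld with 1–2 samples |
| AUC0-t, AUC0-t/dose | several, to form an area | none | withheld with 1–2 samples |
| λz, t½, AUC0-inf, AUC0-inf/dose, CL/F, Vz/F | 3, through λz | 3 | little or nothing |

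Only in the first row does the restriction lack an estimation reason. No bias is claimed for AUC0-t.

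**2. Day 1 active subjects (single-dose plus multiple-dose).** 50 µg: 3. 100 µg: 3+9 = 12. 200 µg: 6+9 = 15. 400 µg: 6+9 = 15. Total 45. Pooling the two parts is an assumption; SAP 15.2 allows it but does not require it.

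**3. One withheld value at 50 µg.** With 3 actives and 3 values required, a single loss takes 50 µg below the threshold. If each 50 µg subject has probability q of only 1–2 quantifiable samples, the chance is 1−(1−q)³: 14% at q = 5%, 27% at 10%, 49% at 20%, 66% at 30%, 88% at 50%. For the pooled 100 µg group of 12 it is under 2% even at q = 50%.

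**4. How close to the LLOQ could 50 µg be?** The LLOQ is not given, but the 4-hour expectation in SAP 15.1 bounds it. Assume one compartment with absorption rate 8/h, exposure proportional to dose, and the expectation holding for the median 400 µg subject. Then the median 50 µg Cmax is at most [Cmax/C(4 h)] ÷ (400/50) times the LLOQ.

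| Half-life (h) | Cmax/C(4 h) | ÷ 8 = largest 50 µg Cmax/LLOQ |
|---|---|---|
| 0.5 | 146 | 18 |
| 0.6 | 62 | 7.8 |
| 0.75 | 27 | 3.3 |
| 1 | 11 | 1.4 |

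The only half-life anchor is the rat: AUC/Cmax = 12.1/13.8 = 0.88 h (Protocol 1.2.1), and 0.88 × ln 2 ≈ 0.6 h if the decline is mono-exponential.

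**5. Simulated Cmax slope.** Assumptions: true slope 1, the model in step 4, CV 60%, 10% residual error, SAP sampling times, pooled Day 1 numbers, and any dose with fewer than 3 values dropped. Ranges span half-lives 0.5–1 h and repeated runs.

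| Median 50 µg Cmax/LLOQ | As worded | With the fix |
|---|---|---|
| 2 | 0.87–0.96 | 0.96–0.98 |
| 3 | 0.94–0.98 | 0.99–1.00 |
| 5 | 0.98–1.00 | 0.99–1.00 |

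At 2× the low end belongs to a half-life of 0.5 h and the high end to 1 h. Step 4 rules out 1 h at 2×. With CV 40% at 2×, the slopes are 0.95–0.99 and 0.99–1.00.

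At 2×, 16–49% of 50 µg subjects have only 1–2 quantifiable samples and a further 9–11% have none. The 50 µg dose has fewer than 3 Cmax values in 58–94% of trials as worded, against 25–29% with the fix. It has fewer than 2, so N/A under SAP 6.1, in 64% of trials at half-life 0.5 h and 18% at 1 h. If the threshold instead means that the model is not run, no Cmax slope is reported in those 58–94% of trials.

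**6. Where the worst bias arises.** At 2× and 0.5 h, 50 µg is dropped in about 94% of trials, and the slope in those trials is still about 0.88–0.89. The bias there comes mostly from truncation at 100 µg.

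**7. Against precision.** The 90% half-width is t·σ/√Sxx, with σ = √ln(1+0.6²) = 0.555. With 50 µg: 1.681 × 0.555/√18.64 = 0.22. Without it: 1.684 × 0.555/√12.87 = 0.26, and the dose range falls from 8-fold to 4-fold. The largest bias, 1−0.87 = 0.13, is about 0.6 of the 0.22 half-width.

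**The case against.** The best defence is that the effect may be nil. LLOQ, human half-life and CV are all assumed above. If every subject has at least three quantifiable samples, the rule never acts. At 5× the LLOQ the effect is negligible, and even at 2× the bias lies inside the confidence interval. The case-by-case clause might also be thought to let the pharmacokineticist keep a Cmax. The point about size stands and sets the severity. The point about the clause does not: it asks whether data are sufficient, and nothing in it lifts a minimum stated as required.

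Four stronger readings might be inferred, and the documents do not support them:

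- *The low values are hidden.* They are not. SAP 15.1 keeps them in the listings, the individual plots and the by-time summaries, with BLQ set to zero.
- *An inflated 50 µg mean is what flattens the slope.* In the worst case 50 µg is usually out of the model (step 6), and often its summary would be N/A.
- *The 20% extrapolation rule for AUC0-inf is a fault of the same kind, and the subject set for CL/F and Vz/F is undefined.* The 20% limit is a prespecified reliability rule under which AUC0-inf "will be listed but not included in summary and inferential" statistics, and SAP 15.2 lists the subjects concerned. It excludes only AUC0-inf; SAP 5.3 supplies the set for the rest. The largest distortions that can be simulated for AUC0-inf need a half-life that conflicts with the 4-hour expectation.
- *Dose escalation is affected.* SAP 4.1 names only safety data for that review. SAP 3.1 lets PK data support an added higher dose within a safe exposure limit, but no passage ties that to the slope.

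**Conclusion.** The point holds as a minor correction. The text applies a three-sample requirement to three parameters that need one sample, and no other section removes it. The direction of the effect is clear: the lowest observed Cmax values are lost, first at 50 µg and then at 100 µg.

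The size is conditional. It matters if the median 50 µg Cmax is about two to three times the LLOQ, fades by five times, and rests on the assumed CV, half-life, pooling and dropping of doses with too few values. The missing statement about such doses is a gap whatever the LLOQ, because 50 µg starts with exactly the number required.

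**What to change.** In SAP 15.2, before unblinding:

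1. State that Cmax, Cmax/dose and Tmax are reported for any subject with at least 1 quantifiable post-dose concentration. Keep the three-point minimum for AUC0-t and the λz-dependent parameters. Footnote, by dose, the number of subjects with no quantifiable sample.
2. In the same edit, state whether a dose with fewer than 3 values is dropped from the power model or the model is not run for that parameter.

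The cost is SAP wording and minor programming. A Cmax from a sparse profile is slightly less precise. Subjects with no quantifiable sample still cannot enter a geometric mean or a log-scale model, so a small bias remains (slope 0.96–0.98 in the 2× case). If every profile has three or more quantifiable samples, the first change alters nothing.
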